5.5 Pharmacokinetic (PK) population

The PK population includes all randomized subjects who receive at least 1 dose of study drug and who have at least 1 postdose value of plasma concentration to be included in the PK analysis without important protocol deviations which may affect the PK of study drug. PK analysis will only be performed on samples with active study drug.

6 STATISTICAL CONSIDERATIONS

6.1 Descriptive Statistics

Continuous data will be summarized descriptively using the number in the analysis set (N), the

number of observations (n), mean, standard deviation (SD), median, minimum and maximum. Categorical data will be summarized using frequency counts and percentages. The denominator for the percentages will be the total number of subjects in the treatment group and analysis population being presented, unless otherwise specified (e.g. on some occasions, percentages may be calculated out of the total number of subjects with available data at a particular visit and/or time point).

Unless otherwise specified, all data will be summarized by analysis visits and treatment group.

6.2 Statistical Tests

Unless otherwise specified, all formal statistical tests of treatment effects will be done at two-sided significance level of 0.05. Point estimates will be accompanied with two-sided 95% CIs where applicable.

7 DATA CONVENTIONS

Data will be handled as follows except for the results of blinded data review meeting (BDRM).

7.1 Analysis Variable Definitions

7.1.1 Study Subjects

7.1.1.1 Protocol Deviation

Protocol deviations will be documented, reviewed and determined in the BDRM. Protocol deviations potentially influencing the evaluation of the primary endpoint will be defined as major deviations. The major protocol deviations will be selected in this meeting.

At least the following will be included as major protocol deviations:

- I/E criteria violation with significant impact on the primary endpoint
- Took prohibited medication during treatment

The BDRM meeting minutes will serve as the main document for protocol deviations.

7.1.1.2 Demographic and Other Baseline Characteristics

(1) BMI

BMI will be recalculated using the formula below and reported to 1dp.

$$\text{BMI (kg/m}^2\text{)} = \text{weight at screening (kg) / \{height at screening (m)\}^2}$$

(2) SSc Disease Duration

SSc Disease Duration (days) = the date of informed consent – the date of diagnosis (the first non-Raynaud's phenomenon manifestation) + 1

If the date of diagnosis is missing, the first day of the month will be used.

If the the date and month of diagnosis are missing, then the first day of the first month (January) will be used.

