9.3 Inclusion Criteria

Subjects who meet all the following criteria will be considered eligible to participate in the study:

1. Must provide signed and dated informed consent form (ICF) to participate in the study. Subjects must be able to (in the judgment of the Investigator) understand the nature of the study and all risks involved with participation in the study. Subjects must be willing to cooperate and comply with all protocol restrictions and procedures including study visits.
2. Male or female age ≥ 18 years at screening with documented diagnosis of SSc, as defined using the 2013 ACR/European League Against Rheumatism (EULAR) criteria (Appendix 1).
3. Has diffuse cutaneous form of SSc according to LeRoy and Medsger's criteria (Appendix 1).
4. Disease duration ≤ 5 years from the first non-Raynaud's phenomenon manifestation.
5. Has an mRSS of 15 to 45 units at screening and have clinical skin involvement proximal and distal to the elbows, knees, or both or any truncal involvement, with or without face involvement.
6. If disease duration is > 24 months defined as time from the first non-Raynaud phenomenon manifestation, subject must fulfil at least 1 of the criteria listed below that are indicative of active disease at screening:
 - a. A documentation of new skin involvement that occurred within the past 9 months, or
 - b. Increase in mRSS ≥ 3 units within the past 9 months, or
 - c. Presence of tendon friction rubs (TFRs) or,
 - d. C-reactive protein ≥ 6 mg/L, or
 - e. Erythrocyte sedimentation rate ≥ 28 mm/hr, or
 - f. Platelet count $\geq 330 \times 10^9/L$ (330,000/microliter).

NOTE: Investigator should exclude all other acute intercurrent illness if subjects fulfilling laboratory criteria (d, e, f) only.

7. Willing to follow restrictions regarding concomitant medications that are described in Appendix 2.

8. Female subjects who are non-lactating and have a negative urine pregnancy test at baseline visit prior to receiving the first dose of study drug.
9. Female subjects of childbearing potential and male subjects with partner of childbearing potential currently using/willing to use 2 effective methods of contraception including barrier method as described in Appendix 3.

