MI Step 2: The imputed datasets generated with the approach described above do contain only non-missing values. Non-parametric analysis using The Hodges-Lehman estimator will be performed for ACR CRISS score on each of the 50 generated imputed datasets. The ACR CRISS score at each visit (Weeks 16, 26, 39, and 52) from two treatments groups will enter the corresponding analysis. The Location shift estimate and two-sided 95% confidence intervals will be obtained using the Hodges-Lehman estimator corresponding to Wilcoxon's rank sum test. The paired comparison between each MT-7117 dose level with placebo will also be performed using this non-parametric analysis method. The following SAS code will be used:

[REDACTED]

[REDACTED]

[REDACTED]

[REDACTED]

MI Step 3 : Finally, the MIANALYZE procedure in SAS will be applied to combine the results from these analyses to derive an overall estimate of the treatment differences at W16, ..., W52 according to the following code. In addition to the estimates, corresponding 95% confidence intervals and p-values will be calculated.

The following example SAS code will be used:

*Combine LS mean difference estimates;

[REDACTED]

[REDACTED] TDERR;
RUN;

Prespecified Subgroup Analysis

The treatment effect on the primary endpoint of CRISS score up to Week 52, the secondary endpoint of change from baseline to Week 52 in mRSS and new Revised CRISS up to Week 52 across different subgroups will be explored based on the ITT population for the following subgroups.

Baseline CRP (<6.0, >=6.0, mg/dL)

Baseline ESR (<28, >=28, mm/hr)

Baseline Platelets (<330, >=330, x10^9/L)

Baseline SSc disease duration (<=3 years, >3 and <=5)

Baseline mRSS score (<25, >=25)

[REDACTED]
[REDACTED]
[REDACTED]

Concomitant medication (MMF, no-MMF)

Concomitant medication (Immunosuppressant(IM)*, non-IM)

Baseline disease duration and concomitant medication (<2 years+MMF, <2 years+no-MMF, >=2 years+MMF, >=2 years+no-MMF)

Region (North America, Europe)

MC1R variant (number of MC1R variants, e.g. 0, 1, 2, or 3 and each MC1R variant (MC1R variant: n≥3))

[REDACTED]
[REDACTED]

Baseline %pFVC (>50% and <=80% , >80%)

*Immunosuppressant(IM): methotrexate, leflunomide, azathioprine, mycophenolate and mycophenolic acid

The impact of MT-7117 dose reduction to efficacy

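### Partial SSc onset dates are set to the earliest possible day, so an eligible subject's derived disease duration can exceed 5 years and fit neither prespecified duration subgroup

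*SAP*

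**What the plan says.** SAP 7.1.1.2 takes SSc disease duration in days as the informed consent date minus "the date of diagnosis (the first non-Raynaud's phenomenon manifestation) + 1". It then gives two rules for incomplete onset dates. The first is "If the date of diagnosis is missing, the first day of the month will be used", which I read as the day being missing, since a month must be known for the rule to work. The second applies when the month is missing as well: "then the first day of the first month (January) will be used".

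Protocol 9.3, inclusion criterion 4, measures eligibility from the same event: "Disease duration ≤ 5 years from the first non-Raynaud's phenomenon manifestation".

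SAP 8.2.1 uses duration in two prespecified subgroup definitions, for the CRISS score, change in mRSS and new Revised CRISS. One is "Baseline SSc disease duration (<=3 years, >3 and <=5", with no category above 5 years. The other combines duration with mycophenolate use, cuts at 2 years and has no upper bound: "Baseline disease duration and concomitant medication (<2 years+MMF, <2 years+no-MMF, >=2 years+MMF, >=2 years+no-MMF".

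SAP 8.1.4 also summarises disease duration descriptively at baseline. Neither document caps the imputed duration at 5 years or says where a derived value above 5 years belongs.

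**The concern.** Both rules choose the earliest date consistent with what was recorded, so the error runs in one direction. Someone who truly meets the 5-year criterion can be derived as having more than 5 years of disease and then fits neither category of the first duration subgroup. Others move from the earlier-disease to the later-disease category, at 3 years in the first definition or at 2 years in the second.

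At stake is the reading of the duration subgroups. The rule shifts some earlier-disease subjects into the later group, can leave some of the longest-duration subjects unclassified, and raises the reported baseline duration. With 36 subjects planned per arm, a few such subjects are noticeable within a subgroup.

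**Working it through.** The plan states no figure for this point, so there is none to reproduce.

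**Inputs from the documents.** The duration formula and imputation rules (SAP 7.1.1.2), the 5-year limit (protocol 9.3), the cuts at 2, 3 and 5 years (SAP 8.2.1), and 72 planned subjects (protocol 9.1).

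**Assumptions.** True duration is uniform on 0 to 5 years, missingness is unrelated to duration, and a year is 365.25 days (the SAP gives no day-to-year conversion). The enumeration below uses every consent day from 1 July 2020 to 30 June 2022 and every eligible onset day before it.

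**Single cases**, all with consent on 15 September 2021:

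| True onset | True duration | Recorded | Imputed onset | Derived duration |
|---|---|---|---|---|
| 20 Nov 2016 | 1761 days, 4.82 years | year only | 1 Jan 2016 | 2085 days, 5.71 years |
| 20 Sep 2016 | 1822 days, 4.99 years | day missing | 1 Sep 2016 | 1841 days, 5.04 years |
| 20 Nov 2018 | 1031 days, 2.82 years | year only | 1 Jan 2018 | 1354 days, 3.71 years |

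The first two are eligible but fit neither category. The third moves from the earlier to the later category.

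**Size of the overstatement (enumeration).**
- Day missing: 0 to 30 days, mean 14.7; zero in 3.3% of cases (true onset on the 1st).
- Day and month missing: 0 to 365 days, mean 182; zero in 0.3% of cases (true onset on 1 January).
- The derived duration is below the true duration in no case.

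**Share crossing a cut.** With uniform true duration, the chance of crossing a given cut is the mean overstatement divided by 5 years.
- Year only: 0.5 / 5 = 10% exceed 5 years, and likewise 10% cross 3 years. These are different people, so 20% are affected. As conditional shares, 0.10 / 0.60 = 17% of those truly at 3 years or less move up, and 0.10 / 0.40 = 25% of those truly above 3 years fall in no category.
- Day missing: 14.7 / 1826.25 = 0.8% at each cut.
- The enumeration agrees: 10.0% and 0.8% above 5 years, with the same shares to one decimal place crossing 3 years and 2 years.

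**Expected numbers among 72.** The share of partial dates is not in the documents, so a range of 5% to 50% is used.
- Year only, above 5 years: 72 × 0.05 × 0.10 = 0.36 to 72 × 0.50 × 0.10 = 3.6.
- Year only, above 5 years or across 3 years: 72 × 0.05 × 0.20 = 0.7 to 72 × 0.50 × 0.20 = 7.2.
- Day missing, above 5 years: 0.03 to 0.3.

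**Mid-period imputation** (15th of the month, or 1 July, not after consent). The mean error falls from 14.7 to 0.7 days and from 182 to about 2 days. The share above 5 years falls from 0.8% to 0.2% and from 10.0% to 2.5%. Misclassification at 3 years for year-only dates falls from 10% to about 5% (mean absolute error 0.25 year; 0.25 / 5). The share above 5 years does not reach zero, so the category boundary must change too.

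**The case against.** The strongest reply is that sites must already establish duration. Criterion 4 sets the 5-year limit, criterion 6 depends on whether duration exceeds 24 months, eligibility is checked at screening and again on Day 1 (protocol 10.1.1 and 10.1.3), and no waivers are given (protocol 9). A subject near 5 years with only a year recorded could often not be confirmed as eligible. This stands: year-only dates are probably rarer near 5 years, and near 2 years, than the calculation assumes. It does not protect the 3-year cut.

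The frequency of year-only dates is also unknown. Neither document gives a rate or shows the case report form field, so the lower end of the range is as admissible as the upper. If only days are missing, the effect is close to nil.

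SAP 7 lets the blinded data review meeting depart from these conventions, so an odd value could be resolved before unblinding. That is possible, but no rule for this case is written. The SAP uses the same earliest-date convention for other dates, such as treatment and interruption dates, but that does not make it unbiased for a duration that is then cut at fixed years.

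A reader might infer that the primary analysis loses subjects. The documents do not support that. The ITT comparison does not use duration, and duration is not among the legible imputation factors (part of that text is redacted), nor in the MMRM or responder model. SAP 8.2.1 describes the subgroup effects as explored. A reader might also infer bias between arms. The imputation does not depend on treatment, and no change in a treatment effect has been shown.

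**Conclusion.** The point holds as a small correction. For partial onset dates the derived duration is never understated, and the closed upper category can leave an eligible subject unclassified. In the duration-by-mycophenolate subgroup subjects can be misclassified at 2 years, but nobody is left out.

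It would go too far to say that duration is always overstated: complete dates are unaffected, and a partial date is exact when the true onset was the 1st of the month, or 1 January for a year-only date. Nor does the SAP say that a subject above 5 years is excluded; it leaves that subject without a place.

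The estimate of about 0.7 to 7 misplaced or unclassified subjects rests on uniform true duration, missingness unrelated to duration and an assumed 5% to 50% of year-only dates. Eligibility checks probably make the number above 5 years smaller. The consequences are confined to exploratory subgroups and the baseline duration summary.

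**What to change.** In SAP 8.2.1, write the upper duration category as >3 years. This alone ensures that nobody is left without a category.

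In SAP 7.1.1.2, impute a missing day as the 15th, and a missing day and month as 1 July. Bound the imputed date so that it is no later than consent and, for subjects confirmed to meet inclusion criterion 4, no earlier than 5 years before consent. State the day-to-year conversion in the same place: with the added day and 365.25 days per year, a complete date exactly 5 years before consent gives 1827 / 365.25 = 5.002 years, so the open category is needed even with the bound.

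The cost is SAP wording and one derivation line before database lock. No new data are needed.

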7.1.1.3 Medical History

Medical history will be coded according to the MedDRA version 25.0 or higher.

7.1.1.4 Prior or Concomitant Medication

Medications will be coded according to the WHO Drug Dictionary (WHO-DD) B3 MAR 2019 version or higher.

(1) Prior Medication

Any prior medication, including prescription and over-the-counter medications, taken within 30 days before screening and all SSc-related medications used since diagnosis will be recorded on the eCRF and source documents. The following information will be collected: name of medication, dose, duration, and reason for use.

(2) Concomitant Medication

Concomitant medication(s) is defined as any medication, other than study drug, which is taken during the treatment period, including prescription, over-the-counter medications, herbals, dietary supplements, and recreational drugs. All concomitant medication(s) taken while the subject is participating in the study will be recorded.

Concomitant medication(s) will be provided only if deemed necessary by the Investigator or the subject's personal physician.

Analysis rules to determine prior medications and concomitant medications

Medications with a stop date before the first date of study drug dosing will be defined as prior medications. Medications with start date or stop date on or after the first date of study drug dosing or ongoing up to week 56 will be defined as concomitant medications.

If the medication start date is incomplete, then it will be imputed as follows for the purpose of determining concomitant use:

- If the start date is completely missing, the start date will be equal to the first dose date.

However, if the stop date is not missing and is before the first dose date, then the stop date will be used instead of the start date. It will not be considered as concomitant medications.

- If the start date is missing, the first day of the month will be used.
- If the start date and month are missing, then the first day of the first month (January) will be used.

If the medication stop date is partial, then it will be imputed as follows for the purpose of determining concomitant use:

- If the stop date is completely missing and the medication is not ongoing, the stop date will be equal to the last dose date or date of completion/withdrawal, whichever is the latest.
- If the stop date is missing, the last day of the month will be used.
- If the stop date and month are missing, then the last day of the last month (December) will be used.

7.1.1.5 Treatment Duration and Compliance

(1) Treatment Duration

Study medication exposure in days will be calculated for each subject using the following:

Treatment duration (days)

=Date of last study drug up-to week 52 – date of first study drug + 1

If the date of the first study drug or the date of the last study drug is missing, the first day of the month will be used.

If the date and month of the first study drug or the those of the last study drug are missing, then the first day of the first month (January) will be used.

Interruptions, compliance, and dose changes are not taken into account for duration of exposure.

(2) Treatment Compliance

Treatment compliance will be calculated using the formula below and reported to 1dp.

Treatment compliance(%)

$$= \frac{\text{Treatment duration (days)} - \text{Days of missed doses} + \text{Days of overdose}}{\text{Treatment duration (days)}} \times 100\%$$

Days of missed doses : Counted days only if the patient does not take at least 1 of the daily dose

of 3 investigational product tablets

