13.3 Treatment Compliance

The prescribed dosage, timing, and mode of administration of study drug will not be changed. Subjects will be asked questions regarding the compliance, any departures from the intended regimen will be recorded in the eCRF.

Study drug accountability and subject compliance will be documented throughout the double-blind treatment period using study-specific study drug dispensing and return record forms. For subjects who do not return their blister wallets, the site will question each to determine compliance (e.g. number of doses missed since the last visit).

Subjects will be asked to return all unused medication including empty and partially used wallets. Study drug dispensed at the previous visit will be retrieved by the Investigator or designee and compliance assessed by returned medication count.

Non-compliance will be defined as taking $\leq 80\%$ or $\geq 120\%$ of study drug during any evaluation period (from any visit to the following visit).

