7.1.1.6 Interruption duration

Study drug interruption duration will be calculated for each subject who experienced study drug interruption using the following:

Interruption duration (days) = End Date of Study Drug Interruption – Start Date of Study Drug Interruption + 1

If the Start Date of Study Drug Interruption or the End Date of Study Drug Interruption is missing, the first day of the month will be used.

If the date and month of the Start Date of Study Drug Interruption or the those of the End Date of Study Drug Interruption are missing, then the first day of the first month (January) will be used.

Drug Interruption : if all 3 investigational product tablets per day are not taken.

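### A partial last-dose or interruption-end date is set to the start of its month or year with no floor at the start date, so durations can be too short or negative; the missed-dose day also has two readings.

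*SAP*

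**What the plan says.** **Duration.** SAP 7.1.1.5 defines treatment duration as "Date of last study drug up-to week 52 – date of first study drug + 1". The same section gives one rule for both ends of treatment. When the day of the first dose or of "the date of the last study drug is missing, the first day of the month will be used". When day and month "are missing, then the first day of the first month (January) will be used". SAP 7.1.1.6 does the same for interruptions: when "the End Date of Study Drug Interruption is missing, the first day of the month will be used", and 1 January if the month is also missing. Neither section says that an imputed end date may not precede the start date, and neither uses the last visit as a bound.

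**Other end dates in the SAP.** For concomitant medication, SAP 7.1.1.4 says "If the stop date is missing, the last day of the month will be used", or the end of December when the month is missing. SAP 7.1.3.1 treats adverse event stop dates in a similar way, using the last observed date when the event stopped in that same month.

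**Compliance.** SAP 7.1.1.5 takes treatment duration, subtracts days of missed doses, adds days of overdose and divides by treatment duration. A missed-dose day is defined as "Counted days only if the patient does not take at least 1 of the daily dose" of three tablets. Days of overdose are not defined there. Protocol 13.3 has "compliance assessed by returned medication count", with a site enquiry about missed doses for subjects who do not return their wallets. Protocol 13.1.2 has a similar provision that records the number of days missed.

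**The concern.** The first of the month is a usual choice for a partial start date, because it is the earliest day consistent with what is known. Applied to an end date, it shortens the interval as far as possible and can put the end before the beginning. The SAP uses the opposite convention for its other stop dates and gives no reason for the difference.

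Partial dates are plausible in two settings. For subjects who terminate early and do not return, the last-dose date is collected by telephone (Protocol 9.5 and 10.1.4). Interruptions for a repeat pregnancy test, a nevus evaluation or a repeat laboratory test (Protocol 10.1.3.3) may start and end within one month.

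On compliance, a day is either missed or not, and the text does not say clearly which days count as missed. Two programmers could therefore place the same subject on opposite sides of the 80% limit in SAP 8.1.9.

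At stake are the exposure, compliance and interruption summaries (SAP 8.1.9 and 8.1.10) and the adverse event tables by treatment duration (SAP 8.3.1).

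**Working it through.** The documents give no exposure or compliance figure to reproduce, so the check applies the SAP's formulas to example subjects. All dates below are illustrations.

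**1. Durations.** Duration = end date - start date + 1, with the end date imputed as in SAP 7.1.1.5 or 7.1.1.6.

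| Case | True duration | Duration under the SAP rule |
|---|---|---|
| First dose 31 Mar 2021, last dose 30 Mar 2022, day missing | 365 | 336 (end set to 1 Mar 2022) |
| Same, day and month missing | 365 | 277 (end set to 1 Jan 2022) |
| First dose 20 Aug, last dose 30 Aug, day missing | 11 | 1 - 20 + 1 = -18 |
| First dose 15 Mar, last dose known only to the same (non-leap) year | positive, not known | -73 + 1 = -72 |
| Interruption from 10 June, end known only as June | 1 to 21 | 1 - 10 + 1 = -8 |

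The largest understatement is 31 - 1 = 30 days with the day missing (30/365 = 8% of a full course). With day and month missing it is 364 days (31 December set to 1 January). If the true day is uniform over a 31-day month, which is an assumption, the mean understatement is 15 days.

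**2. Exposure categories.** SAP 8.1.9 divides days by 30.4375. A course from 10 March to 28 June 2021 is 111 days (111/30.4375 = 3.65 months). With the day of the last dose missing it becomes 84 days (84/30.4375 = 2.76 months), which moves it from the 3-to-6-month band to the band up to 3 months. The lowest band begins at 0, so a negative duration fits none.

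**3. Partly taken doses.** Protocol 13.2 specifies three tablets once daily. Tablet compliance = tablets taken / (3 x days). SAP compliance without overdoses = (days - missed days) / days. Reading A: a day is missed if no tablet is taken. Reading B: a day is missed if at least one of the three is not taken.

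| Pattern over 365 days | Tablet count | Reading A | Reading B |
|---|---|---|---|
| 2 of 3 tablets every day | 2/3 = 66.7% | 100% | 0% |
| 2 of 3 tablets on 110 days, 3 on the other 255 | (765 + 220)/1095 = 90.0% | 100% | 255/365 = 69.9% |

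In the first row, reading A counts as compliant a subject who is non-compliant under Protocol 13.3. In the second, reading B counts as non-compliant a subject who is compliant by tablets. The definition of a drug interruption in SAP 7.1.1.6 has the same two readings.

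**The case against.** **The date errors are conditional.** They need a partial date, and no frequency is given. The first dose is taken at a clinic visit, and sites are told to obtain the last-dose date. A negative duration from a missing month also needs the start and end to fall in the same calendar year. SAP section 7 makes its conventions subject to the blinded data review meeting, so an impossible date can be corrected before unblinding. All of this stands, and it keeps the point small. The meeting does not replace a rule, though: a negative value would be noticed, whereas a 365-day course recorded as 336 days would not.

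**The comparison rule serves another purpose.** The medication stop-date rule is for determining concomitant use, not for measuring time. That is true, but the adverse event stop-date rule is expressly used for duration as well.

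**Day counts have support in the protocol.** Protocol 13.1.2 and 13.3 provide for asking about missed days or doses, and SAP section 1 says that its analysis details supersede the protocol's. So a reader should not infer that counting days is foreign to the protocol. It is the fallback for unreturned wallets. What remains is that the SAP uses it throughout, does not list this in section 10, and words it ambiguously. Reading A may be the more natural one, but the text does not settle it.

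**Overdose days.** A reader might infer that adding overdose days is a flaw of the day count, because they cancel missed days. The documents do not support that. With 20 of 70 days missed and 20 doubled, the formula gives (70 - 20 + 20)/70 = 100%. A tablet count gives (30 x 3 + 20 x 6)/(3 x 70) = 210/210 = 100%. Both are net measures, as are the protocol's two-sided limits.

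**Conclusion.** The date rule is wrong for end dates as written. Where a last-dose or interruption-end date is partial, it understates duration by up to 30 or 364 days and permits negative values. It is also at odds with the SAP's other stop-date rules. The missed-dose-day definition is a secondary fault: it is open to two readings, which in the extreme case score 100% or 0% where the tablet count is 67%.

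Two wider conclusions should not be drawn. Exposure is not wrong in general: fully recorded dates are unaffected, and a partial first-dose date under the same rule errs the other way and overstates exposure. Nor are the efficacy results at risk: the primary analysis does not use these variables. Compliance is not among the major deviations named in SAP 7.1.1.1, although that list is a minimum. The point is minor but cheap to correct. Its actual size depends on how many dates are partial and how often doses are partly taken, neither of which the documents give.

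**What to change.** **Dates (SAP 7.1.1.5 and 7.1.1.6).** Keep the first-of-period rule for start dates only. Impute a partial last-dose or interruption-end date to the latest possible day, capped at the last visit or the completion/withdrawal date (and at Week 52 for treatment duration), and never before the start date. The cap matters, because an uncapped end-of-month rule could overstate exposure by up to 30 days.

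**Compliance (SAP 7.1.1.5).** Where wallets are returned, use tablets taken divided by 3 x days in the period. Where they are not, use the site's missed-dose enquiry, because dispensed minus returned would count every unreturned tablet as taken. Define missed days and overdose days wherever days are still counted, and clarify the interruption definition in 7.1.1.6 in the same way. List any remaining departure from Protocol 13.3 in SAP section 10.

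**Cost.** A few sentences in the SAP before database lock. The date rule needs no new data. Tablet accountability is already required (Protocol 13.1.6 and 13.3), but the documents do not say that the counts are in the analysis database, so the sponsor should confirm this before adopting the tablet-based formula.
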